11.4.8. EDSS scores

Descriptive statistics of the EDSS scores, will be presented by treatment group and visit.

11.4.9. Categorical change from baseline in EDSS Score

A subject's EDSS change is defined as the difference between the subject's EDSS score at Baseline, and his or her last non-Baseline recorded EDSS score. EDSS changes will be classified as "Worsening", "Unchanged" or "Improvement".

The counts and percentages of subjects in each category will be presented by treatment group and visit.

In addition, counts and percentages of the categorical change from study LAQ/5062 baseline will be presented.

11.5. Safety And Tolerability Assessments

11.5.1. Adverse Events

The incidence and frequency of AEs will be presented by System Organ Class and preferred terminology according to the Medical Dictionary for Regulatory Activities (MedDRA) dictionary. AEs will also be presented by System Organ Class, High Level Term and preferred terminology.

Data will be tabulated by treatment group, gender, age, maximal severity, maximal outcome, maximal action taken and maximal relationship to the tested drug.

SAEs and seriousness criteria will be listed and discussed on a case by case basis.

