ARR = annualized relapse rate, EDSS = expanded disability status scale, MSFC = Multiple Sclerosis Functional Composite, GdE = gadolinium enhancing

The observed clinical benefits of laquinimod indicate a distinctive efficacy profile with a pronounced effect on disability which appears to be larger than that predicted by the common relationship between relapse rate and disability observed for other disease modifying therapies ([Sormani et al 2010](#)). This effect was consistent between the 2 studies (EDSS; ALLEGRO: 35.9% [p=0.0122], BRAVO: 33.5% [p=0.04¹]. In addition, treatment with laquinimod demonstrated reduction in brain atrophy: ALLEGRO: 32.8% [p<0.0001], BRAVO¹: 27.4% [p<0.0001]).

On 30 December 2015 the DMC for the LAQ-MS-305 (CONCERTO) and TV5600-CNS-20006 (ARPEGGIO) studies held an unscheduled meeting to review cardiovascular events. The DMC found an imbalance in serious cardiovascular events in the high dose treatment arms (1.2 mg in CONCERTO, 1.5 mg in ARPEGGIO). Due to these events and the DMC recommendation to stop all laquinimod treatment arms above 0.6 mg in the MS trials, the 1.2 mg treatment arm in the CONCERTO study was discontinued as of 01 January 2016. The risk/benefit balance of this dose was considered negative at that point.

The DMC did not identify any overt cardiovascular risk in the 0.6 mg treatment arm, but felt that long term monitoring for emergence of any signal is necessary. Therefore, the 0.6 mg treatment arms in the CONCERTO and ARPEGGIO studies will be continued while the sponsor closely monitors cardiovascular events in all laquinimod studies, such as this one. This is discussed further in Section [3.4.1.7](#).

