3.4.1.7. Cardiovascular Events (Laquinimod 1.2 and 1.5 mg)

On 30 December 2015, a DMC review of 8 unblinded cases from the CONCERTO and ARPEGGIO studies found an imbalance in serious cardiovascular events in the high dose treatment arms in the study: 6 cases in the CONCERTO 1.2 mg treatment arm, compared to no events in the 0.6 mg or placebo treatment arms, along with a cerebral infarct in a 31-year old man on the 1.2 mg treatment arm. In the ARPEGGIO study, 1 heart attack event was identified in the laquinimod 1.5 mg treatment arm. The decisions were largely based on data from 15 November 2015 when total exposure in CONCERTO was 3070 patient-years in 2199 individuals and total exposure in ARPEGGIO was 35 patient-years in 191 individuals.

Due to the above, the 0.6 mg treatment arm will be continued in the CONCERTO and ARPEGGIO studies while the sponsor closely monitors cardiovascular events in all laquinimod studies, including the present study. Additional measures implemented in this protocol amendment include an additional emphasis on disallowed medications, medications and stopping rules for organ impairment (ie, factors which may increase laquinimod exposure), as well as regular evaluation and treatment management of major modifiable cardiovascular risk factors, and collection of unscheduled blood samples, eg, for clinical laboratory tests.

The DMC also recommend that study subjects continuing on laquinimod 0.6 mg be re-consented with information about the cardiovascular risk seen in higher doses.

Currently the mechanism of the cardiovascular events remains unknown. Although no specific time-to-event patterns have been identified, cardiovascular risk factors and demographics may play a role. Different pre-existing risk factors were noted, including hypertension, high cholesterol, and/or smoking history. While all cases exhibited signs of myocardial tissue injury, the cardiac work-up in these cases revealed heterogeneous etiologies. Of note, the cases all had some established cardiovascular risk factors, including patients with probable myocarditis or with probable familial hypercholesterolemia. Further investigation into potential predictors and the potential causality are ongoing.

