10.1. Protocol-Defined Adverse Events for Expedited Reporting

Ischemic cardiac events (such as myocardial infarction, unstable angina, acute coronary syndrome etc), and cerebrovascular events (such as cerebral arterial occlusion, cerebral ischemia, etc) should be reported to the sponsor within 48 hours, including completion of the corresponding dedicated CRF.

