11. STATISTICAL METHODOLOGY

A total of up to 264 subjects, randomized to treatment with 0.3 mg or 0.6 mg of laquinimod, are expected to be recruited into this double-blind, multi-national trial. The trial is planned for 36 weeks of double-blind treatment.

All data summaries in this trial will be presented by treatment group.

The statistical analyses of this study will be exploratory in nature. Continuous variables will be presented by descriptive statistics (mean, standard deviation, minimum, median and maximum values), by treatment group. For categorical variables treatment group counts and percentage from total subject population will be tabulated.

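### The Section 10.1 cardiovascular category is split across AE rows with no rate or interval, so the planned outputs will not state what event rate on 0.6 mg is excluded

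*Combined protocol and SAP*

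**What the plan says.** Section 3.3.2 reports that the DMC for CONCERTO and ARPEGGIO saw no overt cardiovascular risk at 0.6 mg but "felt that long term monitoring for emergence of any signal is necessary". Section 3.4.1.7 brings this trial into that effort: "the sponsor closely monitors cardiovascular events in all laquinimod studies, including the present study".

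Section 10.1 turns this into data collection. It names "Ischemic cardiac events (such as myocardial infarction, unstable angina, acute coronary syndrome etc), and cerebrovascular events" as one category, which "should be reported to the sponsor within 48 hours, including completion of the corresponding dedicated CRF".

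On analysis, Section 11.5.1 says "The incidence and frequency of AEs will be presented by System Organ Class and preferred terminology". It adds a version with High Level Terms, breakdowns by treatment group, gender, age, severity, outcome, action taken and relationship, and this: "SAEs and seriousness criteria will be listed and discussed on a case by case basis". Section 11 opens with "The statistical analyses of this study will be exploratory in nature" and presents categorical data as counts and percentages of subjects. It describes 36 weeks of double-blind treatment and sets out no analysis of the open-label phase, apart from noting in Section 11.2 that all subjects then receive 0.6 mg. Nowhere does it mention a grouped cardiovascular count, a patient-year denominator or a confidence interval.

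**The concern.** The category exists at the point of collection and disappears at the point of analysis. Cardiac and cerebrovascular events go to different organ classes, and within each class to different terms. With few events expected, the output will be rows of zeros and ones.

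Percentages of subjects add a second problem. Open-label follow-up has no fixed end, since it lasts as long as the sponsor continues development. The same 0% could therefore rest on one year of exposure per subject or on eight. A reader of the planned tables cannot tell a zero that is informative from one that is not, and the question put by the DMC concerns exactly that difference.

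**Working it through.** **Inputs from the documents**
- 110 ongoing subjects when Amendment 10 was issued (Section 21.1).
- CONCERTO (Section 3.4.1.7): 6 cases plus 1 cerebral infarct at 1.2 mg, none at 0.6 mg or on placebo; 3070 patient-years over all arms.
- ARPEGGIO (same section): 1 event at 1.5 mg.
- Table 3: myocardial infarction under cardiac disorders, cerebrovascular accident under nervous system disorders.

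**Assumptions, not in the documents**
- Two-sided 95% level.
- 110 subjects on 0.6 mg with no dropout, followed for 1 to 8 years.
- The 1.2 mg arm held one quarter to one half of the CONCERTO exposure, with one third as the middle case.

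**Step 1: the plan's own figures.** The plan gives no rate, margin or precision for these events, so there is nothing to reproduce. The one count that can be checked agrees: 6 + 1 + 1 = 8 cases, as Section 3.4.1.7 states.

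**Step 2: what a small count would exclude.** The exact Poisson upper limit for x events in T patient-years is χ²(0.975; 2(x+1)) / (2T). The numerator term χ²/2 is 3.689 for x = 0 and 5.572 for x = 1. Upper limits per 1000 patient-years:

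| Years × 110 subjects | Patient-years | 0 events | 1 event |
|---|---|---|---|
| 1 | 110 | 33.5 | 50.7 |
| 2 | 220 | 16.8 | 25.3 |
| 3 | 330 | 11.2 | 16.9 |
| 5 | 550 | 6.7 | 10.1 |
| 8 | 880 | 4.2 | 6.3 |

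A crude percentage would not move with follow-up: 0/110 has an exact upper limit of 3.3% in every row.

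**Step 3: an indicative benchmark.** Seven events at 1.2 mg:
- share 1/2: 7/1535 = 4.6 per 1000 patient-years
- share 1/3: 7/1023 = 6.8 (exact 95% CI 2.8 to 14.1)
- share 1/4: 7/767.5 = 9.1

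With zero events, the limits after 1 and 3 years (33.5 and 11.2) lie above this whole range of point estimates.

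**Step 4: how easily a zero arises.** If the true rate were 6.84 per 1000, the probability of no event is exp(−0.00684 × 110) = 0.47 over 110 patient-years and exp(−0.00684 × 330) = 0.10 over 330.

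**Step 5: exposure needed.** To exclude 6.84 with zero events takes 3.689/0.00684 ≈ 540 patient-years, or 4.9 years for 110 subjects. Over the assumed shares the range is about 404 (for 9.12) to 809 (for 4.56) patient-years, or 3.7 to 7.4 years.

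**The case against.** A reader might infer that the data cannot show which rate is excluded. The documents do not support that. Section 10 has AE onset dates recorded, and Section 15.2 requires source records of when the IMP was started and completed, so a bound can be calculated at any time. What is missing is its prespecification and reporting. If it is calculated later, the event group and denominator are chosen after the events are known.

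A reader might also take long-term surveillance at 0.6 mg to be the declared purpose of Amendment 10. Section 21.1 gives the primary purpose as additional safety measures, such as re-consent, stopping rules for organ impairment and GFR monitoring; expedited reporting is one item in that list. Monitoring for a signal is the stated context in Sections 3.3.2 and 3.4.1.7, and it spans all laquinimod studies. Section 3.4.2.3 cites over 10000 patient-years at 0.6 mg, to which 110 subjects add about 1% per year. This study alone is not the instrument that will settle the question. That point stands and limits the gain. It does not remove it, because consistently defined events and patient-years from each study are what a pooled estimate needs.

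Nor would the events go unseen. Most infarctions and strokes should meet the SAE criteria in Section 10 and so be listed and discussed individually. The Medical Monitor, the pharmacovigilance unit, an internal safety committee and external DMCs also review safety data (Sections 18.4.6 and 18.4.7, Appendix 8). This weakens the worry about scattered rows, but a listing gives neither a rate nor a bound.

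Finally, the analyses are declared exploratory and no endpoint has an interval. The omission contradicts nothing in the plan. An interval is descriptive, however, and needs no hypothesis test.

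**Conclusion.** The point holds as a gap between collection and planned reporting. The protocol defines a cardiovascular category in the context of monitoring for a signal at 0.6 mg, then plans outputs that divide it and do not state what rate is or is not excluded. It is a cheap improvement, not a defect that undermines the study.

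The size depends on the assumptions shown. On exposure after Amendment 10 only, zero events over 1 to 3 years would be compatible with the rate implied for the discontinued 1.2 mg arm. That benchmark is soft: its denominator rests on an undocumented arm share, and its cases are not limited to ischemic events, since Section 3.4.1.7 mentions probable myocarditis. Dropout would widen every limit in the table. Adding earlier open-label exposure would narrow them, but the documents do not give its amount and those events predate the dedicated CRF.

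Even a narrow interval would not by itself show the presence or absence of a signal. The open-label phase has no comparator, and the documents give no background rate.

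**What to change.** Add to Section 11.5 an analysis of the Section 10.1 events:
- one prespecified group with a fixed MedDRA term list, with cardiac and cerebrovascular events also shown separately;
- subjects with an event, patient-years on 0.6 mg, rate per 1000 patient-years and exact Poisson 95% CI over the open-label period;
- exposure and events before and after Amendment 10 in separate columns, because ascertainment differs;
- the conclusion worded as the rate that the upper limit excludes, with a statement that this study alone gives a weak bound.

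The cost after the amendment is a term list and about one table from data already collected. Earlier events would have to be drawn from the general AE and SAE records, so that column costs somewhat more and is less secure. The drawback is that the interval will be wide and will reassure less than a bare zero, which is an accurate picture of what the study can say.

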11.5.2. Laboratory Data

The incidence of laboratory tests outside the normal range and the incidence of measurements of potential clinical significance will be presented by treatment group. Shift analysis of these counts from LAQ/5062 baseline and LAQ/5063 baseline will also be provided. Descriptive statistics as well as their changes from LAQ/5062 baseline and LAQ/5063 baseline, will also be presented by study group.

11.5.3. ECG

The incidence of abnormal measurements will be presented by treatment group. Shift analysis from LAQ/5062 baseline and LAQ/5063 baseline will be provided as well. Descriptive statistics, as well as, their changes from LAQ/5062 baseline and LAQ/5063 baseline, will also be presented by study group.

11.5.4. Vital Signs

Incidence of measurements of potential clinical significance will be presented by study group. Shift analysis from LAQ/5062 baseline and LAQ/5063 baseline will be provided as well. Descriptive statistics of vital signs, as well as, their changes from LAQ/5062 baseline and LAQ/5063 baseline, will be presented by study group.

11.5.5. Drug Tolerability & Drop-Out Assessment

The number and percentage of subjects who failed to complete the study will be presented by treatment groups.

The number and percentage of subjects who prematurely discontinued from the study due to AEs will be presented by treatment groups.

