	Female subjects of childbearing potential who may want to get pregnant in the future, and are interested in re-starting laquinimod treatment following delivery and cessation of breastfeeding, may be able to re-enroll in the study after meeting inclusion/exclusion criteria. Re-enrollment will be permitted on a case-by-case basis. Notwithstanding, Teva is under no obligation to re-enroll such subjects and reserves the right to re-enroll or reject enrolment of such returning subjects for no reason and on its sole discretion. A new informed consent form should be signed before re-enrollment.
Relapse Treatment	Allowed treatment for relapse is a fixed dose of 1 g/day IV methylprednisolone or oral steroids for a maximum of 5 consecutive days.
Outcome Measures	
Safety
 
 • AEs • Physical examinations • Vital signs and ECG • Clinical laboratory parameters 
Tolerability
 
 • Number and percentage of subjects who prematurely discontinued from the study • Number and percentage of subjects who prematurely discontinued from the study due to AEs 
Efficacy
 
 • Relapse Rate • The proportion of relapse free subjects • Number of enhancing lesions on T₁-weighted images • Number of new T₂ lesions • Volume of T₂ lesions • Number of new hypointense T₁ lesions • EDSS score

Outcome Measures	Ancillary Studies 
• Pharmacokinetic Study (PK): maximum plasma concentration (C_{max}), time to C_{max} (t_{max}), area under the concentration by time curve (AUC) and elimination rate constant (λ) will be calculated.• PPK: Fitness of a population model to different covariates will be evaluated. 
A separate PK and PPK protocol will be prepared for PK/PPK analysis.

Statistical Considerations	An estimate of sample size is not applicable, since it is an active extension study. Summary statistics will be prepared for demographic, safety and efficacy variables.

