4. STUDY OBJECTIVES

- To make treatment with laquinimod available to all subjects who previously participated in LAQ/5062 study and those who completed the Termination visit of LAQ/5063 active double-blind phase (completion of the full 36 weeks or as requested by the Sponsor).
- To assess the long-term safety, and tolerability in the group that received active treatment in LAQ/5062 protocol and additional short term safety and tolerability in the group who received placebo treatment. LAQ/5063 OL phase will assess long-term safety and tolerability of 0.6 mg laquinimod once daily.

Further efficacy data will be obtained by comparing baseline to termination in the group who received placebo treatment in LAQ/5062 core study protocol.

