Subjects will undergo MRI scans at Baseline (Week 0 / Termination (Week 36) of Core Study LAQ/5062), and Week 36 (Termination visit of LAQ/5063 active double-blind phase [completion of the full 36 weeks or as requested by the Sponsor]). For the open-label phase MRI will be performed at baseline (Month 0 / Termination visit of LAQ/5063 active double-blind phase (completion of the full 36 weeks or as requested by the Sponsor), Month 12 and Month 24. Subjects who performed the MRI scan within the past 14 days as part of the Termination visit of LAQ/5063 active double-blind phase (completion of the full 36 weeks or as requested by the Sponsor), will not need to undergo another MRI scan for baseline visit of LAQ/5063 OL.

Subjects who discontinue treatment for any reason will continue follow-up according to scheduled visits.

Unscheduled visits may be conducted whenever required due to various reasons, for example, AEs, or possible exacerbation.

Figure 1: Treatment Groups in MS-LAQ/5062 (Core Study) and the Double-Blind and Open-Label Phases of LAQ/5063 (Extension Study)

[figure not shown]

[figure not shown]
[figure not shown]
Figure 2: Study Flowchart for MS-LAQ/5062 Core Study

Figure 3: Study Flowchart for Open-Label Phase of LAQ/5063 Extension Study

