7.3.3. Termination Visit

Termination Visit (6) / (Week 36 ± 3 days) of LAQ/5063 Active Double-Blind Phase (Completion of the full 36 weeks or as requested by the sponsor), or any Termination or Early Discontinuation visit occurring as long as the Sponsor continues the development of laquinimod 0.6 mg for RRMS.

In the event of early discontinuation, standard termination procedures will be followed.

Early discontinuation is defined as withdrawal from the study prior to the completion of the full study period:

- Withdrawal prior to completion of 24 months of the first period of open label phase.
- Subjects that chose to continue to the second period of open label phase (additional 36 months), and did not complete this period.
- Subjects that chose to continue treatment from Month 60 as long as the Sponsor continues the development of laquinimod 0.6 mg for RRMS and did not complete this period.

Subjects who are discontinued from study treatment will be encouraged to continue all scheduled visits and procedures until completion of the study (with the exception of procedures associated with drug dispensing and accountability, pregnancy testing, and GFR estimation [including body weight measurement]).

Subjects who have completed 24 months of open label phase and chose not to continue to further extension of open label phase will be regarded as completers.

Subjects who have completed 60 months of the extension open label phase and chose not to continue to further extension of open label phase (as long as the Sponsor continues the development of laquinimod 0.6 mg for RRMS) will be regarded as completers.

The reason for discontinuation of therapy will be documented in the source documents and captured on the CRF. If there are several reasons for early discontinuation, the more severe will be chosen as the primary reason. In the event that laquinimod is discontinued early, an early termination visit should be completed as close to the last dosing date as possible.

Subjects who did not complete the 36 weeks of treatment of LAQ/5063 active double-blind phase until approval of amendment No 2 will be called for an a termination visit of the active double-blind phase as requested by the Sponsor to be switched to the open-label phase (LAQ/5063 OL)

In case a subject completed the 60 months OL period, but decided not to proceed with the further extension, he/she will be considered as completer.

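### Since Amendment 10, the tolerability counts, worded as leaving the study, may miss subjects who stop drug for an adverse event but stay in follow-up

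*Combined protocol and SAP*

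**What the plan says.** The Synopsis and section 4.1.2 list two tolerability outcomes: premature discontinuation from the study overall, and "Number and percentage of subjects who prematurely discontinued from the study due to AEs". Section 11.5.5 analyses them as "The number and percentage of subjects who failed to complete the study will be presented by treatment groups" and "The number and percentage of subjects who prematurely discontinued from the study due to AEs will be presented by treatment groups". None of these places counts subjects who stop study drug.

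Section 4 makes tolerability an aim of the open-label phase: "LAQ/5063 OL phase will assess long-term safety and tolerability of 0.6 mg laquinimod once daily".

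Sections 5.1, 7.1 and 7.3.2 each state: "Subjects who discontinue treatment for any reason will continue follow-up according to scheduled visits". Sections 7.3.3 and 7.3.4 put it more softly, as encouragement to continue visits. The log in 21.1 dates this follow-up to Amendment 10 and does not list 11.5.5 among the sections changed.

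Section 7.3.3 gives the definition: "Early discontinuation is defined as withdrawal from the study prior to the completion of the full study period".

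**The concern.** For an oral drug taken over years, the event of interest for tolerability is that a subject could not go on taking it. While stopping drug and leaving the study generally went together, a count of leavers was a fair proxy. Amendment 10 separates the two events and leaves the count as it was.

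A subject who stops 0.6 mg because of an adverse event and then attends every remaining visit has, on the literal wording, neither left the study nor failed to complete it. The better the new follow-up works, the more of these subjects the tolerability percentages would miss. If sites read the text differently, the count would also depend on local practice.

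**Working it through.** The plan gives no figure to reproduce: the analyses are descriptive and there is no sample-size calculation. The check is mainly a comparison of texts.

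**Text under which a drug stop with continued visits is not counted**
- Synopsis, 4.1.2 and 11.5.5: both counts concern leaving, or not completing, the study.
- 7.3.3, lead sentence of the definition: early discontinuation means withdrawal from the study.
- 5.1, 7.1 and 7.3.2: a subject off treatment continues scheduled follow-up.
- 7.3.4: the early termination visit is for subjects who leave and will not or cannot continue visits. Its list of reasons, which includes adverse events, is a list of reasons for withdrawal from the study.
- 7.3.4.1.3 (cancer): study drug is stopped, and no termination visit is mentioned.

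**Text under which it would be counted**
- 7.3.3, third bullet of the definition, which is tied to continued treatment: "Subjects that chose to continue treatment from Month 60 as long as the Sponsor continues the development of laquinimod 0.6 mg for RRMS".
- 7.3.3, on the visit: "In the event that laquinimod is discontinued early, an early termination visit should be completed as close to the last dosing date as possible".
- Appendix 10, items 1.1.3 and 1.2.1: a drug stop under the liver rules is paired with an early termination visit.

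The two groups conflict on what triggers the early termination visit: stopping drug in 7.3.3 and Appendix 10, leaving the study in 7.3.4. No sentence says how 11.5.5 handles a subject who is off drug but in follow-up.

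**Size**

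Let u be the number of subjects who stop drug for an adverse event after Amendment 10, stay in follow-up and are not recorded as having left. Let N be the denominator.

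Understatement in percentage points = 100 × u / N

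- N = 110 (subjects ongoing at Amendment 10, section 21.1): u = 1 gives 100/110 = 0.91.
- N = 264 (upper limit on recruitment, section 11): u = 1 gives 100/264 = 0.38.

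The documents do not give u. As an illustration only, assume 2, 5 or 10 adverse-event drug stops among the 110:

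| Assumed drug stops | Drug-stop count | Left-the-study count, none stay | Left-the-study count, all stay |
|---|---|---|---|
| 2 | 2/110 = 1.8% | 1.8% | 0% |
| 5 | 5/110 = 4.5% | 4.5% | 0% |
| 10 | 10/110 = 9.1% | 9.1% | 0% |

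**The case against.** The strongest reply is that 7.3.3, read as a whole, already treats stopping drug as early discontinuation. Its third bullet concerns continued treatment, it moves between discontinuing therapy and early discontinuation as if they were one thing, and the entry criteria for the later open-label period define completion by months of treatment. This is a reasonable reading, but 7.3.4 blocks it by reserving the termination visit for those who leave. The text supports both readings, and that is the problem.

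A second reply is that the outcome is defined as leaving the study, so a literal count is correct for that outcome. That is true as a matter of definition. But the outcome is listed under tolerability, and these are the only named tolerability outcomes. On that reading the percentage understates the number of subjects who could not continue the drug.

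Third, section 11 is written mainly around the 36-week double-blind phase. The double-blind comparison and withdrawals before Amendment 10 are indeed unaffected. The outcomes in the Synopsis and 4.1.2 are not limited to one phase, however, and section 4 makes open-label tolerability an objective.

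Several points stand. The analyses are exploratory, and no decision rule depends on this count. Action taken is recorded for each adverse event (section 10) and tabulated (11.5.1), so some drug stops may show there, though not as the tolerability outcome and not for all causes. Differences between sites are inferred from the text: the CRF pages and completion instructions are not in the documents, and data review might remove some of the differences.

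**Conclusion.** The concern holds. As written, the plan does not settle whether a subject who stops drug for an adverse event after Amendment 10 and stays in follow-up enters the tolerability counts. On the literal reading the subject does not, and the percentages are too low as a measure of drug tolerability.

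The size cannot be estimated from the documents and may be zero. It depends on two unknowns: how many such drug stops occur, and how many of those subjects stay without being recorded as having left. Neither 110 nor 264 is stated to be the open-label denominator, so the per-subject figures only show scale.

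Confidence is medium because the CRF is not visible. The point should be fixed: it bears on a stated objective, and the change is small.

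**What to change.** In the Synopsis, 4.1.2 and 11.5.5, define and report for the open-label phase the number and percentage of subjects who permanently discontinued study drug, for any cause and for adverse events. Use the reason for discontinuing therapy that 7.3.3 already requires on the CRF. Report withdrawal from the study as a separate item.

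Reconcile the termination-visit text in 7.3.3 and Appendix 10 (1.1.3 and 1.2.1) with 7.1, 7.3.2 and 7.3.4, so that every site records a drug stop in the same way. Which visit rule applies is for the sponsor to decide; the new counts do not depend on it.

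The cost is wording in those sections and no new data for the counts. The one downside is that the reported percentage may be less favourable.
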